2.2 Primary endpoints

- 1. What is the difference in total healthcare costs per patient and in total in patients with iatrogenic trigeminal nerve injury seen in our department according to cause of injury, injured nerve and outcome (temporary or permanent injury)?
 - A temporary injury will be defined as an injury that completely recovered with no more symptoms and clinical exam parameters within the normal limits during one of the consultations during the follow up period.
 - Permanent injury will be defined as an injury where no significant improvement in symptoms or clinical exam parameters was seen during one of the consultations during the follow up period.
- 2. What is the average productivity loss in days in patients with iatrogenic trigeminal nerve injury seen in our department according to cause of injury, injured nerve and outcome (temporary or permanent injury)?
- 3. Amount of medication use per medication class per patient in patients with iatrogenic trigeminal nerve injury seen in our department according to cause of injury, injured nerve and outcome (temporary or permanent injury)?

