2.3 Secondary endpoints

- 1. Are symptoms or clinical exam parameters (2 pointdiscrimination, directional sense, light touch, percentage of dermatome affected, pinprick threshold), MRCS classification and Sunderland classification predictive of a temporary or permanent injury? If so, which parameters can be withheld?
- 2. When an injury is present we will evaluate following parameters according to cause of injury, injured nerve branch and between temporary or permanent injury
 - Demographic data: age, gender
 - Symptoms, pain descriptors, interference with lifestyle
 - Clinical exam parameters (quantitative sensory testing)
 - Outcome & Follow-up: IHS criteria, surgical repair, use of medication
 - Social reimbursement rate and professional status
- 3. If data is present in the patient file regarding legal action taken by the patient against the caregiver who caused the injury this will be registered. We will evaluate how many patients undertook legal action and if they received compensation.
- 4. If sufficient follow up data is present, we will evaluate how long symptoms are present in case of a temporary injury and evaluate evolution of symptoms in relation to time.
- 5. Was imaging performed in light of the injury? If yes, what imaging modality was used (conebeam CT, CT, MRI, orthopantomogram) and did this influence treatment decisions?

- When looking at questionnaires applied in our department: are the results from the
 questionnaires comparable between the different causes of nerve injury, different affected
 branches? Are results comparable between patients suffering from a temporary or
 permanent injury? Following internationally validated questionnaires are part of routine
 examination of pain patients in our department and may be present in the patient KWS
 record:
 - McGill Pain Questionnaire
 - CPAQ-A
 - Brief Pain Inventory
 - EQ-5D
 - GAD-7
 - GCPS,
 - IES-DVL
 - OHIP-49
 - PainDetect
 - PHQ-9
 - PHQ-15
 - PSEQ
 - CPSI
 - IES
 - West Have-Yale Multidimensional Pain Questionnaire
 - Central sensitization inventory
- Is there a correlation between quality of life measured with EQ5D questionnaire and cause of injury, temporary versus permanent injuries, healthcare costs, productivity loss or medication use?

3. Selection and withdrawal of subjects

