(Multivariable) Linear models will be used to evaluate the relations with healthcare costs. In case the period referring to the calculation of the cost differs between subjects, a weighted version of the proposed model will be considered (with the weight being a function of the length of the period. The productivity loss (number of days) will be evaluated with (multivariable) models for count data (e.g. negative-binomial) will be used (with an offset term in case the periods differ between subjects). (Multivariable) logistic regression will be used for the permanent/temporary classification of the injury. In all multivariable models, multiple imputation methods based on the fully conditional specification (FCS) approach (8) will be considered to handle the presence of missing data. In models applied on aggregated data from Belgium and UK, center will be added as a fixed effect and it will be verified if the relations are country dependent.

P-values smaller than 0.05 will be considered significant. Given the multitude of planned analyses, a single significant p-value will be interpreted with caution.

6. Data Management

All medical data, the data collected in the course of the study is treated with the utmost confidentiality. The medical secrecy, the international guidelines (ICH-GCP) and the Belgian legislation are complied with. The investigators undertake to respect the conditions in the European General Data Protection Regulation (Europese Algemene Verordening Gegevensbescherming, AVG) and the Belgian legislation on the protection of natural persons with regard to the processing of personal data.

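### Symptom duration is evaluated only in injuries seen to recover, and temporary/permanent status has no time origin or horizon, so both depend on how long and how often patients were seen

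*Combined protocol and SAP*

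**What the plan says.** **Duration.** Secondary endpoint 4 (section 2.3) states: "If sufficient follow up data is present, we will evaluate how long symptoms are present in case of a temporary injury". It adds a plan to "evaluate evolution of symptoms in relation to time". That second part is not limited to temporary injuries, but no method is named for it. Sufficient follow-up is not defined.

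**Status.** Section 2.2 calls an injury temporary if it "completely recovered with no more symptoms and clinical exam parameters within the normal limits during one of the consultations during the follow up period", and permanent if "no significant improvement in symptoms or clinical exam parameters was seen during one of the consultations during the follow up period". The follow-up period has no stated start, length, minimum or visit schedule.

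**Analysis.** Secondary endpoint 1 asks which findings are "predictive of a temporary or permanent injury". Section 5 (Data Handling) answers with a model: "logistic regression will be used for the permanent/temporary classification of the injury". The same section anticipates unequal observation for two other outcomes. Costs get a weighted model ("In case the period referring to the calculation of the cost differs between subjects") and productivity days get a count model "with an offset term in case the periods differ between subjects". It has no such provision for recovery and names no time-to-event method.

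**Reach.** Temporary/permanent status is also a grouping factor in all three primary endpoints (costs, productivity loss, medication use) and in the questionnaire and EQ-5D comparisons.

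**The concern.** Whether an injury is seen to recover depends on the patient and also on how long and how often the patient was seen. An analysis confined to observed recoverers drops every censored patient. Short follow-up then favours fast recoveries and pulls the observed duration down. Dating recovery to the visit at which it was found pushes it up.

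The status has the same weakness. An unrecovered patient seen once, soon after injury, and one followed for years are not distinguished. Without a horizon, the odds ratios of secondary endpoint 1 describe no fixed quantity, and the groups compared in the primary endpoints are not determined by the text.

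Unequal timing is likely. The Background reports a referral delay of 1 day to 6.5 years (mean 10 months) in an earlier cohort from the same department, and section 2.1 takes patients seen from January 2010 to October 2018.

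**Working it through.** The plan gives no figure to reproduce. The check has three steps.

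**1. Apply the two definitions to patient types.**

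| Course | Temporary? | Permanent? |
|---|---|---|
| Found fully recovered, never unimproved at a visit | yes | no |
| Unimproved at every visit | no | yes, at any time since injury |
| Partly improved, not recovered | no | no |
| Unimproved at one visit, recovered at a later one | yes | yes, if one consultation suffices |

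The classes are not exhaustive. Read literally, they are not exclusive either. If permanent means no improvement at any visit, the overlap goes but the gap stays.

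**2. Duration in observed recoverers (illustration).** From the documents: mean delay of 10 months from injury to first visit. Everything else is assumed:
- 50% of injuries recover. Their recovery time T is Weibull with shape 1.2 and median 12 months, so the scale is 12/(ln 2)^(1/1.2) = 16.3 months.
- Delay D and follow-up F after first visit are exponential.
- A patient is seen only if still symptomatic at referral (T > D).
- With visits every s months, recorded recovery is D + s × ceil((T − D)/s). It is observed only if it is no later than D + F.

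Median months from injury among those seen to recover (3,000,000 simulated injuries):

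| Mean follow-up (months) | 6 | 12 | 24 | 48 |
|---|---|---|---|---|
| Recovery seen at once | 9.5 | 11.6 | 13.5 | 14.9 |
| 6-monthly visits | 13.0 | 14.7 | 16.6 | 18.3 |
| Yearly visits | 17.0 | 18.1 | 19.7 | 21.6 |

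The median in all referred patients who will recover is 17.0. Observed values lie on both sides of it, so the bias has no fixed sign. With 6-monthly visits, the share classed temporary is 6%, 13%, 21% and 28% across the same follow-up lengths, with the recovery process unchanged.

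**3. Status as a logistic outcome (illustration).** Take a predictor with no effect on recovery, 6-monthly visits, and mean follow-up that differs by predictor level. Count every unrecovered patient as permanent.
- 8 v 16 months: 8.9% v 16.6% classed temporary. OR = (0.166/0.834)/(0.089/0.911) = 2.04.
- 11 v 13 months: 12.3% v 14.2%. OR = (0.142/0.858)/(0.123/0.877) = 1.18.
- Equal follow-up: OR = 1.00.

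At 8 v 16 months the OR becomes 1.38 or 0.93 if permanent requires at least 6 or 12 months of follow-up. The unstated classing rule alone moves a null result from about 2 to just below 1. With equal timing it stays at 1.00 under each of these rules.

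**The case against.** **Existing safeguards.** Duration is conditional on sufficient follow-up. Section 5 will consider fully conditional imputation in all multivariable models and promises caution over a single significant p-value. These deserve weight but do not settle the point. The follow-up condition has no threshold and does not govern the status. Imputation sets no horizon and does not class partial improvers. Caution over p-values does not define an outcome. The case report form is a separate file and may hold dates or definitions, but the endpoint text does not refer to it for them.

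**The magnitudes are assumed.** This stands. The documents give neither follow-up lengths nor visit spacing. The Background's 60% persistent disturbance has no horizon, so it cannot calibrate the model. A reader might infer that the planned logistic model will produce false predictors. The documents do not support that: nothing in them suggests a twofold difference in follow-up by predictor level, a small difference gives a small effect, and equal timing gives none. Nor do they support saying that duration will be underestimated, since visit spacing can reverse the sign.

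**The remedy could be too heavy for a chart review.** This stands in part. Setting a time origin, a horizon and exclusive classes does most of the work. A full interval-censored likelihood is one way to handle recovery between visits; dating it to the visit with a sensitivity analysis is acceptable.

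**Conclusion.** The concern holds and should be addressed. Three points follow from the text without any simulation: duration is restricted to observed recoverers, the two classes leave partial improvers out and can overlap, and the status model has no follow-up term although section 5 allows for unequal periods in two other outcomes.

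The numerical size is not known. The range of 9.5 to 14.9 months against 17.0 depends on the assumed recovery curve, the exponential delay and follow-up, and immediate detection of recovery. The duration problem needs no difference between groups to arise. Bias in the odds ratios does need one, and none is documented.

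Because the status also groups costs, productivity loss and medication use, the definition matters beyond the two secondary endpoints. That is a gap in how the groups are formed. It does not show that the primary comparisons are biased.

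**What to change.** 1. **Section 2.2.** State one horizon counted from injury and three classes: fully recovered by then; not fully recovered by then (including partial improvers, also reported separately); and not observed to the horizon (undetermined, not counted as permanent). Use these classes in the primary endpoints and in the questionnaire and EQ-5D comparisons, and report the number undetermined in each group.
2. **Secondary endpoint 4.** Analyse time from injury to full recovery in all patients seen, with delayed entry at the first consultation and censoring at the last symptomatic one. Report recovery by stated times among patients still symptomatic at a stated earlier time, in place of a median in observed recoverers. Allow for recovery lying between two visits, or date it to the visit and show sensitivity to that choice.
3. **Secondary endpoint 1.** Use the same time-to-recovery model, with predictors from the first consultation and centre as a fixed effect. Keep the logistic model at the stated horizon as supportive, adjusted for time from injury to first visit.
4. **Assumptions.** State that results apply to patients seen, not to all injuries, and that loss to follow-up is taken as independent of recovery given covariates.

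**Cost.** Steps 1 and 4 are wording. Steps 2 and 3 need injury and visit dates, and their availability in the merged dataset is unknown. If they are missing there, these analyses fall back to the department's own estimated 400 patients, without the estimated 900 from the second dataset. Patients with a single visit contribute little. With exponential follow-up of mean 12 months they would be 1 − exp(−6/12) = 39% with 6-monthly visits and 1 − exp(−12/12) = 63% with yearly visits. If recovered patients tend not to return, estimated recovery will be too low, and the model cannot correct that.

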3.1 Inclusion criteria

- Presentation with post traumatic, iatrogenic, injury of the trigeminal nerve or its branches (eg. inferior alveolar nerve, lingual nerve)
- latrogenic nerve injury caused by M3 removal, implant placement, orthognathic surgery, endodontic therapy, non-M3 removal, local anesthesia injection, trauma.
- Clinical diagnosis of neurosensory deficit in the distribution of the trigeminal nerve caused by a previous dental or maxillofacial procedure in the vicinity of the affected branch.

3.2 Exclusion criteria

- Neuropathic pain in another region than the trigeminal nerve
- Neuropathic pain not caused by iatrogenic injury

4. Direct access to source data and documents

The selected CRF platform, CastorEDC (www.castoredc.com), permits trial-related monitoring, audit and EC review or regulatory inspection. Source data will be directly accessible to the rightful instance or person on request.

The trial will be conducted in compliance with the principles of the Declaration of Helsinki (current version), the principles of GCP and in accordance with all applicable regulatory requirements. This protocol and related documents will be submitted for review to the Ethics Committee.

The Investigator and the Participating Site shall treat all information and data relating to the Study disclosed to Participating Site and/or Investigator in this Study as confidential and shall not disclose such information to any third parties or use such information for any purpose other than the performance of the Study. All medical data, the data collected in the course of the study is treated with the utmost confidentiality. The medical secrecy, the international guidelines (ICH-GCP) and the Belgian legislation are complied with. The investigators undertake to respect the conditions in the European General Data Protection Regulation (2016/679 Europese Algemene Verordening Gegevensbescherming, AVG/GDPR) and the Belgian legislation on the protection of natural persons with regard to the processing of personal data.

5. Data Handling

Data will be analyzed by [name], statistician at Leuvens Biostatistiek en Statistische Bioinformatica Centrum. Following statistical methods will be applied.

Non-parametric analyses (Mann-Whitney U tests, Kruskal-Wallis tests, Spearman correlations, Fisher exact tests) will be used to compare in a univariable setting the primary and secondary endpoints between groups (e.g. type of nerve) and to evaluate relations between continuous and/or ordinal variables.

(Multivariable) Linear models will be used to evaluate the relations with healthcare costs. In case the period referring to the calculation of the cost differs between subjects, a weighted version of the proposed model will be considered (with the weight being a function of the length of the period. The productivity loss (number of days) will be evaluated with (multivariable) models for count data (e.g. negative-binomial) will be used (with an offset term in case the periods differ between subjects). (Multivariable) logistic regression will be used for the permanent/temporary classification of the injury. In all multivariable models, multiple imputation methods based on the fully conditional specification (FCS) approach (8) will be considered to handle the presence of missing data. In models applied on aggregated data from Belgium and UK, center will be added as a fixed effect and it will be verified if the relations are country dependent.

P-values smaller than 0.05 will be considered significant. Given the multitude of planned analyses, a single significant p-value will be interpreted with caution.

6. Data Management

All medical data, the data collected in the course of the study is treated with the utmost confidentiality. The medical secrecy, the international guidelines (ICH-GCP) and the Belgian legislation are complied with. The investigators undertake to respect the conditions in the European General Data Protection Regulation (Europese Algemene Verordening Gegevensbescherming, AVG) and the Belgian legislation on the protection of natural persons with regard to the processing of personal data.

The CastorEDC (www.castoredc.com) platform will be used to ensure a systematic approach towards entering datapoints after accessing the patient record in KWS. After reading the patient record in KWS, all data will be coded immediately in the CastorEDC database by creating a new and unique identifier, the study ID. A separate patient ID Log file will be kept on a secured UZ Leuven server containing the study ID and patient EAD. After completion of patient inclusion all data entered in CastorEDC will be exported to a coded SPSS database for further statistical analysis without names, initials, date of births, EAD or EMD numbers. The dataset will be password protected and stored on the UZ Leuven server while the study is in progress. Afterwards the study will be deleted from the Castor platform. The password protected SPSS dataset will be stored on the UZ Leuven server for

future research purposes or audits for the next 20 years. The database with research results does not relate to elements such as names, initials, and complete date of birth (dd /mm/yyyy).

Data from the already conducted retrospective study by prof. [name], will be delivered in a secured and coded SPSS dataset without names, initials, or dates of birth and will be manually imported in the CastorEDC platform using separate study specific ID's to allow data merging in 1 CRF platform: CastorEDC. This will allow to conduct retrospective analysis on a larger sample size.

7. Analysis of Healthcare Costs, Productivity Loss, Medication Use

A separate and independent analysis will take place by the R&D department of the Christelijke Mutualiteiten (CM), to analyze health related costs, productivity loss and medication use for these patients. The followed procedure was discussed and agreed upon by all involved parties including the principal investigator, dr. [name], all co-investigators (prof. [name], [name]. [name], [name]. [name]), department of R&D of the CM (represented by dr. [name] and dr. Ing. [name]), CTC legal advisor ([name]) and UZ Leuven Data Protection Officer ([name]). Data collected from KWS records will be used to identify CM members who met the inclusion criteria. An official request by dr. [name], advising physician, (Addendum 2) according to article 26 of KB nr 35 of 20/07/67 (Addendum 3) will ask for additional information on CM-members seen at our department suffering from PTN to further analyze above mentioned endpoints involving injury related costs, productivity loss and medication use within the records of the CM.

Data gathering will include:

The data will be collected by a CM data team using their own records and will be stored in a coded database on their servers. The data results from the CM will be shared with the principal investigator on a secured medium only containing coded results. The followed procedure and legal basis is similar to a previously conducted study by Beutels et al. (9) The database from the CM contains all resource use information of members of the largest sickness fund in Belgium. The membership population of CM corresponds to 43.7% of the total Belgian population. There is a slight bias in favour of the older age groups, but this should not grossly distort the estimates based on this sickness funds. In terms of socio-economic characteristics, the unemployed are slightly underrepresented (40.6% of the unemployed are members), but, again, the overall difference is relatively limited (i.e. 43.7% versus 40.6%), cited from Beutels et al. We estimate 200 records from our department will be eligible for further analysis by the CM.

8. Publication Policy

This retrospective study will be sent for publications in a journal concordant with the subject and after careful considerations with the whole team.

9. Financial Aspects

No external funds are necessary.

10. References

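### The plan applies rank tests and mean-based models to the same primary cost and days-lost endpoints without saying which one answers the question; the rank tests target neither a mean nor a total and carry no period adjustment.

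*Combined protocol and SAP*

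**What the plan says.** Section 2.2, endpoint 1, asks: "What is the difference in total healthcare costs per patient and in total", broken down by cause, nerve and outcome. Endpoint 2 asks: "What is the average productivity loss in days in patients with iatrogenic trigeminal nerve injury seen in our department", with the same breakdown.

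Section 5 (Data Handling) lists "Non-parametric analyses (Mann-Whitney U tests, Kruskal-Wallis tests, Spearman correlations, Fisher exact tests" and says that these "will be used to compare in a univariable setting the primary and secondary endpoints between groups". Primary endpoints are therefore included by name.

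The same section then adds models for exactly these two outcomes. For cost, with the first word in brackets as optional: "Multivariable) Linear models will be used to evaluate the relations with healthcare costs", in a weighted version if the costing periods differ. For days: "The productivity loss (number of days) will be evaluated with (multivariable) models for count data (e.g. negative-binomial) will be used", with an offset if the periods differ. The threshold is 0.05 throughout, with a remark that an isolated significant result should be read cautiously because many analyses are planned.

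The plan does not say which of the two analyses answers endpoints 1 and 2, or what happens if they disagree.

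**The concern.** An average number of days is an arithmetic mean, and a group's total cost is its mean cost times its number of patients. Mann-Whitney and Kruskal-Wallis tests ask a different question: whether patients in one group tend to rank above those in another. In skewed cost data, a few expensive patients can dominate the mean while hardly moving the ranks. If such patients cluster in one group, the rank test can reject although the means are equal, or favour the group with the lower mean.

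Each primary comparison would then carry two p-values that may conflict, with nothing fixed in advance about which one is reported as the finding. At stake is the study's main message: which cause, nerve or outcome carries the greater cost and work loss. Unequal periods add a second problem. The weight and the offset are described for the models only, so a group observed for longer can look more costly in the rank test for that reason alone.

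**Working it through.** The plan gives no effect size, standard deviation or power for these endpoints, so there is no figure of its own to reproduce. The check is of the mechanism.

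**Inputs.** From the documents: a threshold of 0.05 (taken as two-sided; the plan does not say) and about 200 records with cost and days data (section 7). Assumed: lognormal costs; 70 v 105 patients, which is a 40:60 split of 175 (60% is the share with persistent disturbance in the earlier series cited in the introduction); and the CVs below. Each setting used about 4,000 simulated datasets, so the Monte Carlo standard error is at most √(0.5 × 0.5 / 4000) = 0.8 percentage points.

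**Formula.** For a lognormal with mean m and coefficient of variation CV, the log-variance is s² = ln(1 + CV²) and the log-mean is ln m − s²/2. Mann-Whitney responds to

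P(A>B) = Φ( [ln(m_A/m_B) − (s_A² − s_B²)/2] / √(s_A² + s_B²) ).

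It is neutral at 0.5, whatever the means are.

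**Numbers put in.** s² is 0.693 for CV 1, 1.179 for CV 1.5, 1.609 for CV 2 and 2.303 for CV 3.
- Equal means, CV 2 v 1: (0 − 0.458)/1.517 = −0.302, so P(A>B) = 0.38.
- Mean 30% higher in A, CV 3 v 1: (0.262 − 0.805)/1.731 = −0.313, so P(A>B) = 0.38. A has the higher mean but ranks lower.
- Mean 30% higher in A, CV 2 v 1.5: (0.262 − 0.215)/1.670 = 0.028, so P(A>B) = 0.51. The test is almost blind to the difference.

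**Simulated Mann-Whitney results, costs, 70 (A) v 105 (B).**

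| Means | CV, A v B | Result |
|---|---|---|
| Equal | same in both | rejects about 5-6% |
| Equal | 1.5 v 1 | rejects about 35% |
| Equal | 2 v 1 | rejects about 75% |
| A 30% higher | 1.7 or 2 v 1.5 | wrong direction about 0-1% |
| A 30% higher | 2 v 1 | wrong direction about 21% |
| A 30% higher | 3 v 1 | wrong direction about 77% |

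**Days lost, 120 v 80.** Assumed: a share of patients with no days lost, negative-binomial counts (size 1) in the rest, and an overall mean of 20 in both groups.
- Zero share 60% in both groups: Mann-Whitney rejects 5.5%.
- Zero share 70% v 50%: 58%.
- Zero share 80% v 50%: 95%.
- Means 26 v 20 with zero shares 70% v 50%: the group with the higher mean is significantly called lower in 47%.

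A Welch comparison of means rejects in 4.8% and 6.0% in the two settings with equal means and different zero shares.

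**Unequal periods, 80 v 120.** Same cost rate, log-SD 1, period 1.5 times longer in one group: P(A>B) = Φ(0.405/1.414) = 0.61, and Mann-Whitney rejects in about 78%. This comes from the missing adjustment, not from ranking as such: an unadjusted Welch test on the same totals rejects in about 63% (120 v 80).

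Only two-group comparisons were simulated. Kruskal-Wallis works on the same ranks and shares the property, but it was not run.

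**The case against.** The strongest reply is that section 5 already plans mean-based models for both endpoints, with provision for unequal periods, and confines the rank tests to the univariable step. Because the word multivariable is bracketed, unadjusted versions of the models can be read as included. This stands. A reader might infer that rank tests alone decide the primary answer, and the documents do not support that. What is missing is a statement of which analysis governs.

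Second, the large figures need group shapes that differ markedly, and the documents give no distribution. This also stands: with equal shapes the test holds about 5-6%, and with CV 1.7 or 2 v 1.5 the wrong-direction risk is negligible. Shape differences are plausible rather than shown. Endpoint 1 contrasts full recovery with permanent injury, and the introduction reports pain in 54% of inferior alveolar against 10% of lingual nerve injuries.

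Third, the plan advises caution over isolated significant results. That deals with multiplicity. It does not set an order between two analyses of the same question.

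Fourth, the cost question does not use the word mean. Only its total part strictly requires a sum, whereas the days question asks for an average outright.

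Finally, mean comparisons have weaknesses of their own. With CV 3 v 1 and a 30% higher mean, Welch is significant in the right direction in only about 3%. At equal means with CV 2 v 1 it rejects in about 9%.

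**Conclusion.** The point holds as a gap in the analysis hierarchy. Followed as written, the plan yields univariable significance statements on cost and days lost that do not target the stated quantity and are not adjusted for period, next to model results that do target it, with no rule for choosing between them.

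The size depends on assumptions. At equal means, false signals run from about 5-6% (equal shapes) to 75% (CV 2 v 1). With a 30% higher mean, wrong-direction significance runs from about 0-1% to 77%. A 1.5-fold difference in period alone gives about 78%. These rest on lognormal costs and illustrative group sizes, not on data from this study. It would go too far to conclude that the study's findings will be reversed, or that rank tests are invalid here: they are valid comparisons of ordering. The change is worth making because the gap concerns primary endpoints and is cheap to close.

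**What to change.** In section 5, state that the linear model for cost and the count model for days answer primary endpoints 1 and 2. Specify:
- an unadjusted and an adjusted version of each;
- the mean difference or mean ratio with a bootstrap or robust 95% interval;
- how period enters each model. The offset does this for days. For cost, define the outcome per unit of time or otherwise bring period into the mean, because a weight alone changes precision and does not rescale the cost.

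Label Mann-Whitney and Kruskal-Wallis results on cost and days as descriptive, and report medians beside the means. Keep rank tests for ordinal scales and questionnaires. Do not substitute an unstudentised permutation test of means, because unequal shapes distort it too.

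The cost is a few sentences in the plan and a standard bootstrap or robust-variance routine; no new data are needed. The downside is that mean contrasts are sensitive to outlying patients and have low power under heavy skew, so intervals may be wide. The medians show the reader how far a few patients drive the result.
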